5.0 Subject Disposition

The number of subjects for each of the following categories will be summarized, for overall and for each treatment group in ITT Population in Period 1:

- Subjects randomized;
- Subjects who took at least one dose of study drug in Period 1;
- Subjects who completed Period 1;
- Subjects who completed study drug in Period 1;
- Subjects who prematurely discontinued from study in Period 1;
- Subjects who prematurely discontinued study drug in Period 1;

The summary will also be provided for Period 2 for each of the following categories in ITT Population:

- Subjects who entered Period 2;
- Subjects who took at least one dose of study drug in Period 2;
- Subjects who completed study;
- Subjects who completed study drug in Period 2;
- Subjects who prematurely discontinued from study in Period 2;
- Subjects who prematurely discontinued study drug in Period 2;

Number and percentage of subjects who discontinue study drug or who discontinue from study will be summarized by reason (primary reason and all reasons) for each treatment group and overall. Subjects with multiple reasons for premature discontinuation will be counted once in the calculation of the number and percentage of total.

In addition, the above summaries (except for the reason for premature discontinuation) will also be summarized by center in the accountability table.

The number of subjects and percentage of screen failure will be summarized by primary reason.

6.0 Study Drug Duration and Compliance

For each safety population, duration of treatment will be summarized for each treatment group and for all dose groups combined. Duration of treatment is defined for each subject

as last dose date minus first dose date +1. Duration of treatment will be summarized using the number of subjects treated, mean, standard deviation, median, minimum and maximum. In addition, the number and percentage of subjects in each treatment duration interval (≥ 4 weeks, ≥ 12 weeks, ≥ 24 weeks, ≥ 36 weeks, ≥ 48 weeks) will be summarized for ALL_UPA Population.

Treatment compliance will be summarized by treatment groups for Safety_1 Population and upadacitinib dose groups for ALL_UPA Population. Treatment compliance is defined as the number of tablets actually taken divided by the number of tablets that should have been taken. Percent compliance will be summarized.

7.0 Demographics, Baseline Characteristics, Medical History, and Prior/Concomitant Medications

Demographics, baseline or disease characteristics, medical history, and prior and concomitant medications will be summarized overall and by treatment group. Categorical variables will be summarized with the number and percentage of subjects; percentages will be calculated based on the number of non-missing observations. Continuous variables will be summarized with descriptive statistics (number of non-missing observations, mean and standard deviation, median, minimum and maximum).

7.1 Demographics and Baseline Characteristics

Demographics and baseline disease characteristics will be summarized for ITT Population.

Continuous demographic variables include age, weight, height, and body mass index (BMI). Categorical demographic variables include sex, ethnicity, race, age (<40 , $40 - 65$, ≥ 65 years), weight (≤ 100 or > 100 kg), BMI (< 25 , $\geq 25 - < 30$ or ≥ 30 kg/m²), tobacco user (current, former, never, unknown), and alcohol user (current, former, never, unknown).

Disease characteristics include HS disease duration in years, Baseline lesion counts (by lesion type), Baseline skin pain NRS (among all subjects and among subjects with baseline value ≥ 3), Baseline DLQI, Baseline HSSA, Baseline HSIA and Baseline hsCRP as continuous variables, prior exposure to TNF antagonists (yes, no) and baseline Hurley stage ($< III$, III), HS history (anatomic regions, types of lesions) as categorical variables.

7.2 Medical History

Medical history data will be coded using the Medical Dictionary for Regulatory Activities (MedDRA). The actual version of the MedDRA coding dictionary will be noted in the statistical tables and clinical study report. The number and percentage of subjects in each medical history category (by MedDRA system organ class and preferred term) will be summarized overall and by treatment group for ITT Population. The system organ class (SOC) will be presented in alphabetical order, and the preferred terms will be presented in alphabetical order within each SOC. Subjects reporting more than one condition/diagnosis will be counted only once in each row (SOC or preferred term).

7.3 Prior and Concomitant Medications

Prior and concomitant medications will be summarized by generic name in Safety_1 Population. A prior medication is defined as any medication taken prior to the date of the first dose of study drug. A concomitant medication is defined as any medication that started prior to the date of the first dose of study drug and continued to be taken after the first dose of study drug or any medication that started on or after the date of the first dose of study drug, but not after the date of the last dose of study drug. The number and percentage of subjects taking medications will be summarized by generic drug name based on the World Health Organization (WHO) Drug Dictionary for both prior and concomitant medications. Concomitant medications will be summarized for each safety population.

In addition, subjects' prior exposure to antibiotics (systemic and topical), biologics, Jak-inhibitor, and other will be summarized for each treatment group and by reason of discontinuation.

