5.4 Prior and Concomitant Therapy

Any medication or vaccine (including over-the-counter or prescription medicines, vitamins and/or herbal supplements) that the subject is receiving at the time of screening, and/or receives during the study, must be recorded along with the reason for use, date(s) of administration including start and end dates, and dosage information including dose, route and frequency on the appropriate electronic case report form (eCRF). Also, medications taken for HS since date of diagnosis (based on subject recollection and available medical records) should be entered into the appropriate eCRF inclusive of the dates of first and last dose, maximum dosage taken, route of administration.

Any questions regarding concomitant or prior therapy should be raised to the AbbVie Therapeutic Area Medical Director (TA MD)/AbbVie emergency contact. Information regarding potential drug interactions with upadacitinib can be located in the upadacitinib Investigator's Brochure.

Allowed Therapies

Antibiotics

Concomitant use of antibiotics is allowed for the treatment of acute infections during the study. Use of topical or systemic antibiotics to treat HS or other chronic inflammatory disorders is prohibited up to Week 16. After Week 16, concomitant use of any antibiotics for any indication, including HS, is permitted.

Dosing and/or frequency need to be reported in the eCRF documentation; "as needed" (PRN) use is not permitted.

Antiseptic Wash

Subjects are required to use a daily antiseptic wash on their HS lesions for the duration of the study.

Allowable antiseptic washes are limited to: chlorhexidine gluconate, benzoyl peroxide, benzalkonium chloride, or dilute bleach in bathwater.

Wound Care

Use of wound care dressings on HS wounds is allowed. Recommended options include alginates, hydrocolloids, and hydrogels.

Lesion Intervention

Deroofing or STEEP, laser therapy, intense pulse light, local/wide/radical excision, incision and/or draining of lesions, and intralesional injections are allowed after Week 16 assessments. Refer to Section 6.2 for study drug interruption guidelines for elective and emergency surgeries.

Analgesic therapy

If a subject experiences pain (HS- related or non-HS-related) after Baseline, they may initiate analgesic treatment. For HS-related pain, analgesic therapy is limited to the following until after the Week 16 assessments:

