6 STUDY DRUG

6.1 Treatments Administered

Study drug will be taken orally once daily, beginning on Day 1 (Baseline), and should be taken at approximately the same time each day, with or without food.

Study drug includes the investigational product of upadacitinib and matching upadacitinib placebo. Details regarding study drug dosing and administration are provided in the Study Drug section of the Protocol. The study drug will be dispensed at the visits listed in Section 2.1.

Study drug must not be dispensed without contacting the IRT system. Study drug may only be dispensed to subjects enrolled in the study through the IRT system. At the end of the Treatment Period or at the Premature D/C visit, the site will contact the IRT system to provide visit date information and study drug return information for each kit.

AbbVie will not supply any disease-related concomitant medication (indication) therapy taken during the course of the study.

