4.0 Analysis Populations

The following populations will be used for the analyses.

The Intent-to-Treat (ITT) Population includes all randomized subjects. The ITT Population will be used for all efficacy analyses. Subjects will be included in the analysis according to the treatment groups that they are randomized to.

The following populations will be used for the safety analysis:

- The Safety Population in Period 1 (Safety_1) is defined as all subjects who are randomized and received at least one dose of study drug in Period 1.
- The all upadacitinib treated (ALL_UPA) Population is defined as subjects who received at least one dose of upadacitinib in the study. This population will be used to provide a comprehensive summary of safety.

For safety analyses, subjects will be analyzed based on the treatment actually received.

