10.2.1 Treatment-Emergent Adverse Events

For Period 1, treatment-emergent adverse events (TEAEs) are defined as any adverse events that begin or worsen in severity after initiation of study drug through 30 days following the last dose of study drug in Period 1 or first dose in Period 2, whichever is

earlier. For Period 2, TEAEs are defined as any adverse events that begin or worsen in severity after initiation of study drug through 30 days following the last dose of study drug in Period 2. Events where the onset date is the same as the study drug start date are assumed to be treatment-emergent. All TEAEs will be summarized overall, as well as by primary MedDRA SOC and PT. The SOCs will be presented in alphabetical order, and the PTs will be presented in alphabetical order within each SOC.

The number and percentage of subjects experiencing TEAEs will be summarized.

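### SAP 7.3 runs concomitant medication to the last dose of study drug, so the Safety_1 placebo column includes medicines started on upadacitinib 15 mg

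*SAP*

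**What the plan says.** - **Definition (SAP 7.3).** A concomitant medication is one already in use that continued past the first dose of study drug, or one started on or after that date "but not after the date of the last dose of study drug". No period is named.
- **Where it is applied (SAP 7.3).** "Prior and concomitant medications will be summarized by generic name in Safety_1 Population", and then, under the same definition, "Concomitant medications will be summarized for each safety population".
- **Columns.** SAP 7.0 says that "medical history, and prior and concomitant medications will be summarized overall and by treatment group". SAP 10.1 fixes a subject's actual treatment sequence by the regimen received most often in Period 1. For ALL_UPA it plans columns for 30 mg, 15 mg and all upadacitinib subjects together.
- **Safety_1 (SAP 4.0).** It is defined as "all subjects who are randomized and received at least one dose of study drug in Period 1". This says who is in the population, not which data are used.
- **Study drug (Operations Manual 6.1).** "Study drug includes the investigational product of upadacitinib and matching upadacitinib placebo".
- **Design (Protocol synopsis; SAP 2.2).** Treatment lasts 48 weeks. The placebo arm has 12 weeks of placebo and then 36 weeks of upadacitinib 15 mg.
- **Rules that change after Week 16 (Protocol 5.3 and 5.4).** "After Week 16, concomitant use of any antibiotics for any indication, including HS, is permitted". The bars on opioids, on other treatments for HS-related pain and on a named list of other therapies also run only until after the Week 16 assessments.
- **Contrast (SAP 10.2.1).** The Period 1 window for TEAEs is bounded by the "last dose of study drug in Period 1 or first dose in Period 2", with a 30-day tail on the former and the earlier date applying.

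**The concern.** A by-arm table in a population named for Period 1 will be read as describing the placebo-controlled 12 weeks. The definition in SAP 7.3 does not stop there. Two kinds of mixing follow in Safety_1. The placebo column combines time on placebo with time on active drug. Both columns combine weeks under the tight medication rules with weeks under the looser ones. A reader of the study report could not tell from the table whether an HS antibiotic or an opioid listed under placebo was started in Week 6 or in Week 40.

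ALL_UPA has the reverse fault. For a placebo subject the first dose of study drug is a placebo dose on Day 1, so a medicine started and stopped before any upadacitinib was taken still counts under 15 mg.

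What is at stake is the accuracy of a descriptive summary, not an efficacy result.

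**Working it through.** **1. Reproduce the plan's figure.** Total treatment is 48 weeks and placebo is 12 weeks (Protocol synopsis). 48 − 12 = 36 weeks on upadacitinib 15 mg, which agrees with the 36 weeks stated there.

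**2. Find the date that closes the Safety_1 window for a placebo subject.**
- SAP 7.3 closes it at the last dose of study drug.
- Study drug includes upadacitinib (Operations Manual 6.1), so the last dose is the last 15 mg dose in Period 2. For a subject who completes treatment this is about Week 48. Week 48 is inferred from the schedule; SAP 7.3 does not name it.
- Safety_1 has no data cut of its own (SAP 4.0).
- Columns follow the Period 1 regimen (SAP 10.1), so the subject stays under placebo after the switch.

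**3. Shares of a completer's window.**

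| Part of the window | Weeks | Share of 48 |
|---|---|---|
| Period 1 | 12 | 12/48 = 25% |
| Period 2 (15 mg in the placebo arm) | 48 − 12 = 36 | 36/48 = 75% |
| After Week 16 | 48 − 16 = 32 | 32/48 = 67% |

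Ending the window at the Period 1 boundary would leave 12 weeks. The 30 mg column has the same nominal 48 weeks. Its drug does not change at Week 12, but its medication rules do change after Week 16.

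**4. ALL_UPA.** The window opens at the first dose of study drug. For a placebo-arm completer, 12 of 48 weeks (25%) therefore precede any upadacitinib but feed the 15 mg column.

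**5. Illustration of scale (assumption, not a document figure).** Suppose subjects start a medicine at a constant rate, and a proportion q start it within 12 weeks. Over 48 weeks, four such intervals, the proportion is 1 − (1 − q)^4.

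| q over 12 weeks | Over 48 weeks |
|---|---|
| 5% | 1 − 0.95^4 = 19% |
| 10% | 1 − 0.90^4 = 34% |
| 20% | 1 − 0.80^4 = 59% |
| 30% | 1 − 0.70^4 = 76% |

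This applies only to newly started medicines, since those ongoing at first dose count under either window. It describes inflation within a column. With equal rates both columns would rise alike, so it does not measure a between-arm distortion.

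**The case against.** The strongest reply is that a Period 1 table was plainly meant. The population is named for Period 1 and ALL_UPA exists for the comprehensive summary. The first database lock is for Period 1 data (Protocol 7.1, SAP 9.1), and the treatment-duration intervals that reach 48 weeks are planned for ALL_UPA only (SAP 6.0). The SAP also leaves the Period 1 limit unwritten for duration and compliance (6.0), laboratory data (10.3) and vital signs (10.4). The absence of one in 7.3 is therefore weak evidence of a 48-week table.

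The point about intent is fair, and the contrast with 10.2.1 does not prove what the authors wanted. But 7.3 is not silent. It states an end date, and that date falls in Period 2 for anyone who continues. A programmer who follows the text produces the mixed table, and no passage gives a different cut-off for medications.

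Several stronger inferences are tempting, and the documents do not support them:
- *That this table is the planned check on whether the arms differed in co-treatment before the Week 12 readouts.* No passage gives it that role. Antibiotics for HS-related infections count as non-response for HiSCR (SAP 8.0), and analgesic use has dated non-responder rules for NRS30 (SAP 9.4.1).
- *That permitted Period 2 use would be counted as prohibited use.* Appendix A of the SAP gives prohibited medication its own deviation category, and permitted use does not belong in it.
- *That at the Week 12 lock early enrollees would contribute months of Period 2 medication and late enrollees almost none.* This assumes that Period 2 records enter a lock described as covering Period 1. The documents do not say that they do.
- *That all systemic HS therapy is released after Week 16.* Protocol 5.3 keeps one group of systemic therapies barred throughout the study and biologics barred in both periods.

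**Conclusion.** The point holds as a fault in a stated definition with a small consequence. Followed as written, SAP 7.3 gives a Safety_1 placebo column in which 36 of a completer's 48 weeks (75%) are on upadacitinib 15 mg and 32 (67%) fall after Week 16. It also gives an ALL_UPA 15 mg column that includes medicines confined to the placebo period. These shares assume completion of 48 weeks and a full data set; the window is shorter for subjects who stop early. How many extra medicines would appear cannot be derived from the documents.

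Because both arms share the same nominal window, the defect is mixed exposure and mixed medication rules, not unequal planned follow-up. The table is descriptive and no endpoint, test or estimand draws on it, so no efficacy conclusion changes. It is worth correcting because the change is cheap and the table as defined does not describe the placebo-controlled period.

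**What to change.** In SAP 7.3, replace the single window with one for each population.

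- **Safety_1:** count medications taken on or after the first dose of study drug and started before the first Period 2 dose. If the subject took no Period 2 dose, including because Period 2 was not entered, count those started on or before the last Period 1 dose. This follows the Period 1 boundary used for TEAEs in SAP 10.2.1, but is not identical to it, because the medication definition has no 30-day tail.
- **ALL_UPA:** start the window at the first upadacitinib dose and end it at the last. Keep the 30 mg arm's Period 1 medications and the 30 mg, 15 mg and total columns already planned in SAP 10.1. Moving only Period 2 medications into ALL_UPA would wrongly drop the 30 mg arm's first 12 weeks.

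The cost is one sentence in the SAP and a date condition in the program. Protocol 5.4 already requires start and end dates for each medication on the eCRF, so no new data are needed.

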8.0 Handling of Potential Intercurrent Events for the Primary Endpoint

The primary efficacy endpoint, achievement of HiCSR at Week 12 (defined in Section 3.1) will be analyzed in the ITT Population and the following method will be used to address potential intercurrent events:

- Intercurrent events of initiation of antibiotics for HS-related infections and discontinuation of study drug due to lack of efficacy before Week 12 are included in the definition of primary endpoint; subjects who have either intercurrents above will be considered not achieving the response. No other intercurrent events are considered.

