5.3 Prohibited Medications and Therapy

Background Therapies

The following therapies are prohibited until after Week 16 assessments unless otherwise specified:

- 1. Throughout the study, any other systemic therapy that can also be used to treat HS, including but not limited to intramuscular or intravenous corticosteroids, oral corticosteroids equivalent to > 10 mg/day of prednisone, methotrexate (> 25 mg/week), cyclosporine, mycophenolate mofetil, azathioprine, intramuscular gamma-globulin.
- 2. Apremilast, hormonal therapy (except for contraception), metformin (except for continuous treatment of preexisting diabetes), zinc gluconate, colchicine, retinoids, acitretin/etretinate, and fumaric acid esters, methotrexate, and oral corticosteroids are prohibited until after Week 16 assessments.
- 3. New topical therapies used to treat HS (other than protocol-allowed antiseptic) or changes in the concentration/frequency of current topical therapies used to treat HS (including but not limited to exfoliants, e.g., resorcinol).
- 4. Deroofing or skin-tissue-saving excision with electrosurgical peeling (STEEP), laser therapy, intense pulse light, local/wide/radical excision, incision and/or draining of lesions, or intralesional corticosteroid injections.
- 5. Concomitant use of antibiotics (topical or systemic) is not permitted for the treatment of HS or other chronic inflammatory disorders.
- 6. Use of any treatments for HS-related pain, other than ibuprofen or acetaminophen (paracetamol), including but not limited to opioids, antiepileptics (e.g., gabapentin), tricyclics (e.g., nortriptyline), or selective serotonin norepinephrine reuptake inhibitors (e.g., duloxetine, venlafaxine). For non-HS-related pain, all other non-opioid analgesics are allowed at the recommended or prescribed dose per local label. Use of opioid analgesics for HS-related or non-HS related pain is prohibited until after Week 16 assessments.
 - Subjects who are on a documented stable dose and dosing regimen of non-opioid analgesic treatment for at least 14 days prior to the Baseline visit are not permitted to adjust their regimen at least until after the Week 16 assessment. Note: For HS-related pain, analgesic therapy is limited to ibuprofen (as per local labeling, but not exceeding a dose of 800 mg orally every 6 hours and 3.2 g orally every 24 hours) AND/OR acetaminophen (paracetamol) as per local labeling.

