2.0 Study Design and Objectives

2.1 Objectives, Hypotheses and Estimands

The primary objective of this study is to assess the efficacy and safety of upadacitinib 30 mg QD in adult subjects with moderate to severe HS. The primary efficacy objective will be assessed based on the achievement of HiSCR after 12 weeks of treatment with upadacitinib 30 mg when compared to placebo in the Intent-to-Treat (ITT) population, which consists of all randomized subjects.

Hypothesis corresponding to the primary endpoint is:

- The proportion of subjects achieving HiSCR with upadacitinib is greater than that with placebo at Week 12.

The estimand corresponding to the primary endpoint is defined using composite variable strategy:

- Achievement of HiSCR at Week 12 without the initiation of antibiotics for HS-related infections and without premature discontinuation of study drug due to lack of efficacy prior to Week 12.

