The NRI-C will categorize any subject who does not have an evaluation during a pre-specified visit window (either due to missing assessment or due to early withdrawal from the study) as a non-responder for the visit. The only exceptions are: 1) when the subject is a responder both before and after the visit window, the subject will be categorized as a responder for the visit. 2) missing data due to COVID-19 infection or logistical restriction will be handled by Multiple Imputation. Of note, the intercurrent events of initiation of antibiotics for HS-related infections or discontinuation of study drug due to lack of efficacy will lead the subjects being counted as non-responders at later visits. Subjects whose change/percent change from Baseline cannot be calculated because of a missing Baseline will be considered as non-responders at all post-baseline visits. When determining the HiSCR response status, a subject with missing Baseline value will be counted as a non-responder at any post-baseline visit unless a subject's abscess, inflammatory nodule, and draining fistula counts are all zero at a specific visit, where the subject will be a HiSCR responder at that visit. More details are provided in [Appendix E](#).

- A sensitivity analysis for categorical endpoints will use **NRI** with **No** special data handling for missing due to **COVID-19 (NRI-NC)**.

NRI-NC will be performed in the same way as NRI-C without the exception #2 above. That is, missing due to COVID-19 infection or logistical restriction will also be counted as non-responders.

The NRI-C and NRI-NC will not be applicable to experience of flare in Period 1 since it is event-driven.

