9.3.2 Main Analysis of Primary Efficacy Endpoint

Analysis of the primary endpoint will be conducted in the ITT Population based on treatment as randomized. Comparison of the primary endpoint will be made between upadacitinib 30 mg group and historical placebo rate (25%) using a one sample Chi-square test at Week 12. Point estimates, p-value and 95% CIs for the difference in proportions between upadacitinib 30 mg and the historical placebo rate (25%) will be provided.

The attributes of the estimands corresponding to the primary efficacy endpoint are summarized in [Table 1](#).

Table 1. Summary of the Estimand Attributes of the Primary Efficacy Endpoint

Attributes of the Estimand					
Estimand	Treatment	Endpoint	Population	Intercurrent Events	Statistical Summary
Primary efficacy endpoint of HiSCR	Upadacitinib 30 mg QD	Achievement of HiSCR at Week 12 without the initiation of antibiotics for HS-related infections or discontinuation of study drug due to lack of efficacy	All randomized subjects (ITT Population)	The intercurrent of initiation of antibiotics for HS-related infections or discontinuation of study drug due to lack of efficacy are included in the endpoint attribute using composite variable strategy. No other intercurrent event is considered.	Difference between upadacitinib 30 mg and placebo in the proportion of subjects achieving HiSCR at Week 12

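### The HiSCR failure rule names only antibiotics for HS-related infections, an undefined term, and does not state that antibiotics for HS itself, prohibited to Week 16, also count as failure

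*SAP*

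**What the plan says.** **SAP.** The estimand in 2.1 is "Achievement of HiSCR at Week 12 without the initiation of antibiotics for HS-related infections and without premature discontinuation of study drug" for lack of efficacy. Section 8.0 names the same two events, "Intercurrent events of initiation of antibiotics for HS-related infections and discontinuation of study drug due to lack of efficacy before Week 12", scores either one as non-response, and adds: "No other intercurrent events are considered". Table 1 in 9.3.2 repeats the closure: "No other intercurrent event is considered". For NRI-C, 9.2.1 says that "the intercurrent events of initiation of antibiotics for HS-related infections or discontinuation of study drug due to lack of efficacy will lead" to non-response at later visits. The same antibiotic term governs the MI sensitivity analysis (9.2.1), the MMRM exclusions (9.2.2), the Period 2 observed-case summaries (9.2.3) and Appendix E (2.1 and 2.4). The term is not defined in any of these places.

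**Protocol.** Section 5.3 says: "Concomitant use of antibiotics (topical or systemic) is not permitted for the treatment of HS or other chronic inflammatory disorders". Section 5.4 gives the time limit: "Use of topical or systemic antibiotics to treat HS or other chronic inflammatory disorders is prohibited up to Week 16". It also gives the allowance: "Concomitant use of antibiotics is allowed for the treatment of acute infections during the study". After Week 16, antibiotics for any indication, HS included, are permitted. Protocol 7.3 has no antibiotic rule for the primary endpoint.

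**The concern.** The protocol sorts antibiotics by indication into treatment of HS (prohibited) and treatment of acute infection (allowed). The SAP event is written in terms of infection only. Taken at its words, it can fail a subject given an allowed antibiotic for an infected lesion, yet leave as a responder a subject given a prohibited antibiotic for the disease under study.

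If that happens, a response reached with the help of an added HS treatment is credited to upadacitinib. The primary test sets one arm against a fixed 25%, so similar use in the in-trial placebo arm cannot offset it. Even if the authors meant the term to cover HS treatment, whoever derives the primary endpoint has to interpret an undefined indication.

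**Working it through.** **1. Does another rule close the gap?**

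- Apart from the two named events, NRI-C imputes non-response only for a missing evaluation or a missing Baseline. Observed Week 12 counts after HS antibiotics are used as they stand.
- NRI-NC changes only the handling of COVID-19 missingness. The MI analysis keeps the same event definition.
- SAP 4.0 defines no per-protocol population.
- SAP Appendix A counts prohibited medication as a deviation and attaches no effect on response.
- Protocol 5.5 requires study drug to stop after prohibited medication only where continuing would put the subject at risk. Stopping counts as failure only when the reason is lack of efficacy.
- By contrast, for NRS30 both Protocol 7.3 and SAP 9.4.1 score use of a prohibited analgesic as non-response.

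No rule closes the gap for HiSCR.

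**2. The plan's own power figure.** Inputs from Protocol 7.7 and SAP 2.4: n = 40, p0 = 0.25, p1 = 0.57, one-sided alpha 0.05 (z = 1.645).

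Power = Φ[(|p1 − p0|·√n − z·√(p0(1 − p0))) / √(p1(1 − p1))]
= Φ[(0.32 × 6.325 − 1.645 × 0.433) / 0.495] = Φ(2.65) = 99.6%.

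This agrees with the stated figure of more than 95%. The antibiotic rule does not enter it.

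**3. Rejection rule.** Reject when (x − 40 × 0.25)/√(40 × 0.25 × 0.75) = (x − 10)/2.739 exceeds 1.645. That needs x ≥ 15 (z = 1.83; x = 14 gives 1.46). The exact binomial probability of 15 or more at p = 0.25 is 5.4%.

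**4. Illustration under the null.** Assume that the rate under the intended composite is 25% and that a further fraction f of subjects meet HiSCR only after antibiotics for HS and are kept as responders. One subject of 40 is 2.5 points. The rejection probability is P(X ≥ 15 | 40, 0.25 + f):

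| f | Rate counted | P(reject) |
|---|---|---|
| 0 | 25% | 5.4% |
| 2.5% | 27.5% | 11.0% |
| 5% | 30% | 19.3% |
| 10% | 35% | 42.8% |

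SAP Appendix F assumes 45 upadacitinib subjects for its simulations. With that number the critical count is 17, and f = 0, 5% and 10% give 3.9%, 16.4% and 40.2%.

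**5. Illustration at the planned rate.** Assume instead that the 57% includes such subjects and that they are re-scored as failures. P(X ≥ 15 | 40, 0.57 − f) is 99.6% at f = 0, 97.7% at 5% and 91.4% at 10%. Starting from about 23 of 40 responders (57.5%), eight could be re-scored and 15 of 40 would still be significant (z = 1.83, one-sided p = 0.034). The estimate would fall from 57.5% to 37.5%.

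The fractions f in steps 4 and 5 are assumptions. The documents give no frequency of antibiotic use for HS.

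**The case against.** The strongest reply is that the term may have been meant to include antibiotics given for HS. Protocol 2.1 describes HS lesions as having purulent discharge, so a programmer could reasonably class an antibiotic for those lesions as being for an HS-related infection. This stands as far as intent goes: a reader might infer that the SAP has settled on keeping such subjects as responders, and the documents do not establish that. They leave the term open, and the protocol treats HS and acute infection as separate indications.

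A reader might also infer that antibiotics for HS are a likely added therapy, because Protocol 2.1 lists them among HS treatments. The documents do not support that either. The same paragraph says most of the listed treatments are inadequately studied or do not seem very effective. Eligibility criterion 9 requires prior inadequate response or intolerance to oral antibiotics, and Protocol 5.3 prohibits the use. This makes a response produced by oral antibiotics less plausible. It does not exclude topical agents or a different antibiotic.

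Two further points stand in part:

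- The documents do not say how antibiotics for HS were handled in the studies behind the 25%. If such use was counted as response there, the literal rule matches the comparator and a stricter rule would not.
- A comparison with in-trial placebo is planned (SAP 9.3.3), and there the rule applies equally to both arms. It informs on the issue, but it is not the primary test and re-scores nobody.

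**Conclusion.** The point holds as a gap in the definition of the primary estimand. The event is undefined, the list of events is closed, and no planned analysis shows the result with prohibited HS antibiotics scored as failure. Read literally, such a subject remains a responder provided that the Week 12 counts meet HiSCR and study drug was not stopped for lack of efficacy.

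Each affected subject moves the estimate by 2.5 points at n = 40. The larger rejection probabilities in the working should not be read as the trial's error rate. They need both a true rate of exactly 25% and an assumed share of subjects who respond only after HS antibiotics, and the documents support no particular share. At the planned 57% the conclusion of the test is robust. The practical effect is on the size of the HiSCR estimate and on a result close to 15 of 40. This warrants a correction before the Week 12 database lock; it does not threaten the design.

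**What to change.** For Period 1 only, in SAP 2.1, 8.0, 9.2.1, 9.2.2, Table 1 and Appendix E, define the event as *initiation of systemic or topical antibiotics for HS or for an HS-related infection before Week 12*, derived from the recorded reason for use and dates.

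Leave the Period 2 observed-case rule in 9.2.3 as it is. Antibiotics for HS are permitted after Week 16, and carrying the wider definition into that section would drop long-term data after permitted treatment.

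State in SAP 2.4 whether the 25% historical rate was derived under the same antibiotic rule. If it was not, or this is unknown, report the primary comparison under both definitions.

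**Cost.** This is a wording change and one more indication in the derivation. Protocol 5.4 already requires the reason for use and the dates to be recorded, so no new data are needed. The HiSCR rate may fall slightly. Because 9.2.1 and 9.2.2 also govern other Period 1 endpoints, their derivations change too. The change is to the analysis only and leaves clinical management untouched.
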